#### **5.1.5 Definition of maximum tolerated dose**

A dose will be considered non-tolerated and dose escalation will cease if 2 or more of up to 6 evaluable subjects experience a DLT at a dose level. Once the non-tolerated dose is defined the MTD will be confirmed at the previous dose-level below the non-tolerated dose.

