**Table 2 Summary of Dose Cohorts**

Dose Cohort	Number of Subjects	MEDI-573 Dose
1	3-6	5.0 mg/kg as a 60-minute IV infusion once every 7 days
2	3-6	15 mg/kg as a 60-minute IV infusion once every 7 days
3	3-6	30 or 45 mg/kg as a 90-minute IV infusion once every 21 days

Subjects will be enrolled to ensure a minimum of 3 and a maximum of 6 evaluable subjects per cohort. Dose escalation will follow the scheme below, according to the following logic:

If no DLT is observed (for definition see Section 5.1.4) in a cohort of 3 evaluable subjects, then dose escalation may occur. Dose increases will be permitted after review of data from a minimum of 3 evaluable subjects has been performed.

If one subject of the 3 evaluable subjects experiences a DLT, then 3 more evaluable subjects will be enrolled to have 6 evaluable subjects. If only one DLT is observed in the complete cohort of 6 evaluable subjects, then dose escalation may occur.

If 2 or more subjects experience a DLT in a group of up to 6 subjects, irrespective of the number of subjects enrolled, the dose will be considered not tolerated and recruitment to the cohort and dose escalation will cease. If the next lower dose level has 3 evaluable subjects, 3 more evaluable subjects will be enrolled to have 6 evaluable subjects.

At the discretion of the sponsor, an intermediate dose may be chosen for dose escalation. Situations that might prompt selection of an intermediate dose include unexpected toxicities that do not meet the definition of DLT or multiple similar toxicities in a cohort that do not meet the definition of a DLT. If an intermediate dose is chosen, subsequent dose escalation will be to the next predetermined dose provided all the criteria for dose escalation in Rules above are met. Further dose escalation will be based on toxicities observed at each dose level,

Date

and may proceed according to the original dosing schedule or may include additional intermediate dosing steps based on accumulated safety data.

There will be no intra-subject dose escalations.

The dose for subsequent cohorts or a decision to stop recruitment will be agreed by the dose escalation committee (DEC) after review of the data from each cohort (see Section **Error! Reference source not found.**).

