#### **5.1.4 Definition of dose-limiting toxicity**

DLT will be graded according to the NCI CTCAE V4.0 and will be assessed from Cycle 1, Day 1 through Cycle 1, Day 21.

A DLT is defined as:

1. Any Grade 3 or higher non-haematologic toxicity that occurs during the DLT assessment period where a cause other than the investigational product cannot be reasonably justified with the following exceptions:
  - Grade <4 high glucose (fasting) with a duration of <24 hours after administration of MEDI-573
  - Grade 3 fever (in the absence of neutropenia) defined as >40.0°C (39.5°C in the axilla) that resolves to normal or baseline within 24 hours of treatment and is not considered an SAE
  - Grade 3 rigors/chills that respond to optimal therapy
  - Any isolated or transient laboratory changes without associated clinical signs or symptoms.
2. Any Grade 3 or higher haematologic toxicity that occurs during the DLT assessment period where a cause other than the investigational product cannot be reasonably justified.

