### **5.1.7 Dose escalation committee**

The DEC will evaluate the safety and tolerability of MEDI-573 collected in the cohort and decide on whether to proceed to dose escalation for the next cohort.

The DEC will consist of:

- Study Team Physician, who will chair the committee, or delegate
- Principal Investigator or representative(s) of the study sites

Sub Investigator from investigational sites, the Study Pharmacokineticist, Study Statistician, Patient Safety Scientist and Study Delivery Team Leader may also be invited as appropriate. The DEC remit document for this study will define the exact membership and who should be present for decisions to be made.

Once there are at least 3 evaluable subjects at a dose level, the DEC will review and assess all available safety data documented by the investigators, if possible, together with available PK data, such as demography, AEs of CTCAE grade  $\geq 2$  observed in the DLT assessment period (Days 1 to 21 in Cycle 1), and whether the beginning of Cycle 2 for MEDI-573 has to be postponed or not, to make a decision on for the next cohort of subjects. Any dose interruptions will be taken into account.

The decision may be to:

1. Proceed with dose escalation – refer to Section [5.1.3](#)
2. Expand the cohort to a maximum of 6 evaluable subjects
3. Stop the dose escalation part of the study

Any subject started on treatment in error, as he/she failed to comply with all of the selection criteria but meets the criteria of an evaluable subject, will be reviewed on a case by case basis by the DEC to determine if the subject should be included or excluded in the decision for dose escalation.

The decisions and decision-making of the DEC on the next dose level will be documented and give a notice to the principal investigators prior to dosing any new subjects.

Date

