## **5.2 Rationale for dose regimen**

In a preclinical study, MEDI-573 was administered to cynomolgus monkeys repeatedly as an IV infusion at doses up to 60 mg/kg weekly for 13 weeks, and there was no evidence of toxicity. This result indicated that the no observable adverse effect level (NOAEL in cynomolgus monkeys is higher than 60 mg/kg, which is estimated to be equivalent to higher than 19 mg/kg in human on the basis of body surface area of monkey and human (conversion factor 3.1).

In the US study MI-CP184, up to Feb. 17, 2011, twenty-five subjects with advanced solid tumours were enrolled in 6 cohorts in dose-escalation phase and dose expansion phase of 15 mg/kg. There has been ever no DLTs. (See Section 2.2.2). These results demonstrated the safety and tolerability of MEDI-573 administered weekly at doses up to 15 mg/kg. Thus the safety and tolerability of the starting dose of the scheduled Japanese study (5.0 mg/kg) have been demonstrated in Study MI-CP184.

Consequently, since the above results showed the NOAEL in cynomolgus monkeys is estimated to be equivalent to higher than 19 mg/kg in human and the safety of MEDI-573 up to 15 mg/kg was demonstrated in Study MI-CP184. In addition, the regimen (Cohort 3) that is administration of every 21 days is one of the dose regimens is plan to examine in the development program in the future. As for this regimen, it is plan to execute it in the MI-CP184 study.

Whether to proceed and the dose for the next cohort will be determined based on the safety, tolerability and PK data (if available) of MEDI-573 collected in the cohort in reference to the results of Study MI-CP184.

Date

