### **7.2 Determination of sample size**

The primary objective of this study is to investigate the safety and tolerability and thereby identify the MTD of MEDI-573. Hence the number of subjects has been based on the desire to obtain adequate tolerability, safety and pharmacokinetic and PK data while exposing as few patients as possible to the investigational product and procedures.

For each cohort, cohorts of 3-6 evaluable subjects will be required. The total number of subjects will depend upon the number of dose escalations necessary.

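### The MTD rule in Section 5.1.5 ignores schedule, so on the planned ladder a Cohort 3 (every-21-day) failure can label 15 mg/kg weekly the MTD although no higher weekly dose was tested

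*Protocol*

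**What the plan says.** Section 5.1.5 calls a dose not tolerated once two or more DLTs occur among at most six evaluable subjects, and continues: "Once the non-tolerated dose is defined the MTD will be confirmed at the previous dose-level below the non-tolerated dose". Schedule is not mentioned.

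Table 2 in Section 5.1.3 lists Cohort 1 (5 mg/kg every 7 days), Cohort 2 (15 mg/kg every 7 days) and Cohort 3, "30 or 45 mg/kg as a 90-minute IV infusion once every 21 days". After a failure, Section 5.1.3 says: "If the next lower dose level has 3 evaluable subjects, 3 more evaluable subjects will be enrolled to have 6 evaluable subjects". It also contains an option: "At the discretion of the sponsor, an intermediate dose may be chosen for dose escalation". No schedule is attached to either provision.

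Under Section 5.1.4, DLTs on both schedules are judged over the same period; they "will be assessed from Cycle 1, Day 1 through Cycle 1, Day 21". In Section 5.1.7 the dose escalation committee may escalate, expand the cohort or "Stop the dose escalation part of the study"; it is given no rule for naming an MTD.

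On the US study, Section 5.2 concludes: "These results demonstrated the safety and tolerability of MEDI-573 administered weekly at doses up to 15 mg/kg". Section 2.2.2 shows that its weekly cohorts also ended at 15 mg/kg.

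The MTD is the fifth secondary objective in Section 1.2, to be determined if applicable. Section 7.2 ties it more closely to the study's purpose: "The primary objective of this study is to investigate the safety and tolerability and thereby identify the MTD of MEDI-573".

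**The concern.** Taking the level below a failed one as the MTD is sound when levels differ in dose on one schedule. The failed level then bounds the tolerable dose from above and the level beneath bounds it from below. From Cohort 2 to Cohort 3, dose and schedule change together. A failure in Cohort 3 is evidence about single large infusions every 21 days. It does not show that any weekly dose above 15 mg/kg is intolerable.

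Applied as written, the rule would turn toxicity seen only on the every-21-day schedule into an upper limit for the weekly schedule. A reader of the report could take 15 mg/kg weekly as a ceiling established by the trial when it was only the highest weekly dose tried. The rule would also leave the every-21-day schedule without a stated MTD conclusion, although Section 5.2 names that schedule as one planned for future development.

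**Working it through.** **1. The plan's own figure.** Three cohorts of 3 to 6 evaluable subjects give 3 × 3 = 9 to 3 × 6 = 18, as Section 3.1 states. No hypothesis test is planned, so there is no power figure to reproduce.

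**2. The rule at each possible failure (planned ladder).**

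| Cohort that fails | Level named by 5.1.5 | Same schedule? |
|---|---|---|
| 2 (15 mg/kg weekly) | 5 mg/kg weekly | Yes |
| 3 (30 or 45 mg/kg every 21 days) | 15 mg/kg weekly | No |

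Only the second row is at issue.

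**3. Is Cohort 2 below Cohort 3?** Doses from Table 2; dose per 21 days = dose per infusion × infusions per cycle.

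- Cohort 2: 15 × 3 = 45 mg/kg.
- Cohort 3: 30 × 1 = 30, or 45 × 1 = 45 mg/kg.

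Per infusion, Cohort 2 is lower (15 against 30 or 45). Per 21 days it is 45/30 = 1.5 times a failed 30 mg/kg, or equal to a failed 45 mg/kg.

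**4. Exposure in the DLT window (illustration).** The protocol gives no human half-life, so 3.5 to 21 days is assumed, with linear one-compartment kinetics and infusion time ignored. Let k = ln 2 / half-life and A(t) = (1 − exp(−kt))/k. Cohort 2 exposure over 21 days is 15 × [A(21) + A(14) + A(7)]; Cohort 3 exposure is 30 × A(21) or 45 × A(21). The Cohort 2 peak after the third dose is 15 × (1 + exp(−7k) + exp(−14k)), against 30 after one 30 mg/kg dose.

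Worked case, half-life 7 days: kA(21), kA(14) and kA(7) are 0.875, 0.75 and 0.5. Cohort 2 gives 15 × 2.125 = 31.875 and 30 mg/kg gives 30 × 0.875 = 26.25 (both divided by k), a ratio of 1.21. The Cohort 2 peak is 15 × 1.75 = 26.25, and 30/26.25 = 1.14.

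| Half-life (days) | AUC: Cohort 2 / 30 mg/kg | AUC: 45 mg/kg / Cohort 2 | Peak: 30 mg/kg / Cohort 2 |
|---|---|---|---|
| 3.5 | 1.36 | 1.10 | 1.52 |
| 7 | 1.21 | 1.24 | 1.14 |
| 14 | 1.11 | 1.35 | 0.91 |
| 21 | 1.08 | 1.39 | 0.83 |

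The peak ratio crosses 1.00 at a half-life of about 10 days. Against a failed 30 mg/kg, Cohort 2 is therefore higher in window exposure throughout the range, and lower in peak only for half-lives under about 10 days. Against a failed 45 mg/kg, it is lower in window exposure.

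**5. How often Cohort 3 would fail, once opened.** P(fail) = 1 − (q³ + 3pq⁵), with p the true DLT rate and q = 1 − p. At p = 0.20: 1 − (0.512 + 0.197) = 0.291.

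| Assumed p | 5% | 10% | 20% | 30% |
|---|---|---|---|---|
| P(Cohort 3 fails) | 3% | 9% | 29% | 51% |

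**6. The expansion step.** If Cohort 2 passed with 0 of 3 DLTs, Section 5.1.3 adds three subjects after a Cohort 3 failure. The chance that these bring two or more DLTs is 3p²q + p³: 0.096 + 0.008 = 0.104 at p = 0.20, and 0.189 + 0.027 = 0.216 at p = 0.30 (rates assumed). In that case 15 mg/kg weekly is itself not tolerated, and the rule moves to 5 mg/kg weekly, a proper same-schedule result. The problem arises only when Cohort 2 keeps fewer than two DLTs in six.

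**The case against.** Several points on the other side stand.

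- **An inserted level.** The intermediate-dose option in Section 5.1.3 names no schedule. A level inserted before Cohort 3 would become the previous one and could change the dose that 5.1.5 names. The option is discretionary and written for escalation, so it limits the point to the planned ladder without curing the rule.
- **The label is not automatic.** It depends on the expansion in step 6.
- **The MTD's standing.** It is a secondary objective, if applicable, and Section 7.1 lists it together with an optimal biologic dose, if possible. This lowers the stakes. But a failed cohort is exactly when the MTD becomes applicable, and Section 7.2 ties it to the study aim.
- **Likelihood.** Section 5.1.3 lets the US results decide the Cohort 3 dose, and Section 2.2.2 reports no DLT in 25 subjects. Failure may be uncommon. However, only one of those subjects was at 30 mg/kg and none at 45 mg/kg, so the documents do not settle the rate.

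A reader might infer that the every-21-day failure would be hidden. The documents do not support that: Sections 5.1.3 and 5.1.5 require the Cohort 3 dose to be declared not tolerated, and Section 7.9 lists all data by dose cohort. A reader might also infer that 15 mg/kg weekly would be unsafe because it carries more drug per cycle than a failed 30 mg/kg. That is unsupported too: Cohort 2 is judged on its own DLTs, before and after expansion.

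**Conclusion.** The point holds as a fault in a rule the protocol itself fixes, not as a missing detail. It needs three conditions: no intermediate level is inserted, Cohort 3 has two or more DLTs, and Cohort 2 still has fewer than two DLTs in six. Section 5.1.5 then labels 15 mg/kg weekly the MTD with no higher weekly dose tested or failed.

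If 30 mg/kg fails, the named regimen gives 1.5 times the failed dose per 21 days, so its place below that dose is not clear. If 45 mg/kg fails, Cohort 2 equals it in 21-day dose but is lower per infusion and in modelled window exposure, so calling it a lower level is reasonable; the label still does not describe an every-21-day MTD.

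The labelling error follows from Table 2 and Section 5.1.5 alone. The exposure ratios rest on assumed half-lives and linear kinetics, and the failure probabilities on assumed DLT rates; neither is needed for the conclusion. The consequence is confined to the MTD label. Dosing, subject safety and sample size are unaffected. The wording should be corrected.

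**What to change.** Replace the MTD sentence in Section 5.1.5 with:

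> The MTD is the highest dose level below the non-tolerated dose, studied on the same schedule (every 7 days or every 21 days), with fewer than 2 DLTs in 6 evaluable subjects. If no lower dose was studied on that schedule, no MTD is declared for it.

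Add:

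> If Cohort 3 is not tolerated and no lower every-21-day dose was studied, the report states that no tolerated every-21-day dose was found. The highest weekly dose with fewer than 2 DLTs in 6 evaluable subjects after any expansion is reported as the highest weekly dose tolerated, and is called the weekly MTD only if a higher weekly dose was not tolerated.

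In Section 5.1.3, keep the expansion of Cohort 2 after a Cohort 3 failure and describe it as confirming the tolerability of that weekly dose.

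The cost is a few sentences in 5.1.5 and a clause in 5.1.3. No subjects, visits or data are added, and the total of 9 to 18 evaluable subjects stands. Adding a lower every-21-day level would take 3 to 6 more evaluable subjects; that is the sponsor's choice and not part of this correction.

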#### **5.1.6 Definition of evaluable subject**

Subjects are considered evaluable if they receive MEDI-573 and either:

Date

- have received 3 doses of MEDI-573 (Cohorts 1 or 2) or 1 dose of MEDI-573 (Cohort 3) during the cycle and are followed for 21 days from the date of first dose (one cycle)
- have experienced a DLT during the cycle 1

Subjects who have a delay in drug administration during the DLT evaluation period are considered as unevaluable.

### **5.1.7 Dose escalation committee**

The DEC will evaluate the safety and tolerability of MEDI-573 collected in the cohort and decide on whether to proceed to dose escalation for the next cohort.

The DEC will consist of:

- Study Team Physician, who will chair the committee, or delegate
- Principal Investigator or representative(s) of the study sites

Sub Investigator from investigational sites, the Study Pharmacokineticist, Study Statistician, Patient Safety Scientist and Study Delivery Team Leader may also be invited as appropriate. The DEC remit document for this study will define the exact membership and who should be present for decisions to be made.

Once there are at least 3 evaluable subjects at a dose level, the DEC will review and assess all available safety data documented by the investigators, if possible, together with available PK data, such as demography, AEs of CTCAE grade  $\geq 2$  observed in the DLT assessment period (Days 1 to 21 in Cycle 1), and whether the beginning of Cycle 2 for MEDI-573 has to be postponed or not, to make a decision on for the next cohort of subjects. Any dose interruptions will be taken into account.

The decision may be to:

1. Proceed with dose escalation – refer to Section [5.1.3](#)
2. Expand the cohort to a maximum of 6 evaluable subjects
3. Stop the dose escalation part of the study

Any subject started on treatment in error, as he/she failed to comply with all of the selection criteria but meets the criteria of an evaluable subject, will be reviewed on a case by case basis by the DEC to determine if the subject should be included or excluded in the decision for dose escalation.

The decisions and decision-making of the DEC on the next dose level will be documented and give a notice to the principal investigators prior to dosing any new subjects.

Date

### 5.1.8 Guidelines for administration of MEDI-573 (after cycle 2)

It is not allowed to delay or modify during Cycle 1.

Dose interruption or discontinuation of MEDI-573, following the first cycle of treatment, will be determined based on AE (see Table 3 and Table 4). In addition, MEDI-573 be able to continue if events occurred is those clearly attributable to another cause such as disease progression or accident, not clinical significant lab abnormality, and not clinically significant and can be controlled by medication. . In Cycle 2 or greater, dosing interval should be 6 days or longer in Cohorts 1 and 2, and 20 days or longer in Cohort 3.

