### **3.1 Overall study design and flow chart**

#### **Study Design**

This is a Phase 1, open-label, single-arm, dose-escalation study to evaluate the safety, tolerability, and pharmacokinetics of MEDI-573 in Japanese adult patients with advanced solid tumours refractory to standard therapy or for which no standard therapy exists.

The study will be conducted at one site in Japan.

Subjects are considered evaluable if they receive 3 doses of MEDI-573 (Cohorts 1 and 2) or 1 dose of MEDI-573 (Cohort 3) during cycle 1 and are followed for 21 days from the date of first dose (one cycle) or they discontinue MEDI-573 due to dose-limiting toxicities (DLTs). Each cohort will include 3 to 6 evaluable subjects and a total of 9 to 18 evaluable subjects will be evaluated during the study.

MEDI-573 will be administered once every 7 days (on Days 1, 8, and 15 of each 21-day treatment cycle) as a 60-minute IV infusion in Cohorts 1 and 2 and once every 21 days (Day 1 of each 21-day treatment cycle) as a 90-minute IV infusion in Cohort 3 until unacceptable toxicity, documentation of disease progression, or other reasons for subject withdrawal. Intra-subject dose escalation will not be allowed. On 2nd Cycle and beyond, continuation, interruption or permanent discontinuation of treatment will be decided based on the criteria specified in section 5.1.8. Subjects will be considered to have completed a cycle only when they have received all the specified doses at each cycle, and subjects who do not complete a cycle will discontinue the treatment and not move on to the next cycle. Rules for interruption or discontinuation of MEDI-573 in individual subjects are described in Section 5.4.1. Rules for interruption or discontinuation of MEDI-573 and study entry are described in Section 5.4.2.

Dose escalation will follow a standard 3+3 design. Rules for dose escalation are described in Section 5.1.3.

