**Table 5 Study plan (Cohorts 1 and 2)**

Assessment	Screen	Cycle 1					Cycle 2 and Beyond			End of Treatment d	Follow-up		Details in
		Day 1	Day 2	Day 3	Day 8	Day 15	Day 1	Day 8	Day 15		30 days after the last dose	3 months after the last dose	
Allowance (days)	- 28 - 1	—	—	—	—	—	±2	±2	±2		+3	±14	
Written Informed Consent	X						X a						Appendix D
Verify Eligibility Criteria	X	X											4.1, 4.2
Medical History	X												6.3
Pregnancy test b	X	X					X				X		6.3.5
WHO Performance Status	X	X					X			X	X	X c	6.3.2
Physical Examination	X	X					X			X	X	X c	6.3.2
Height	X												6.3.2
Weight	X	X					X			X	X		5.1.2
Vital Signs	X	X		X	X	X	X	X	X	X	X		6.3.3
ECG	X	X					X			X	X		6.3.4
Haematology/ Clinical Chemistry	X	X		X	X	X	X	X	X	X	X		6.3.5
Urinalysis	X	X			X	X	X	X	X	X	X		6.3.5
Tumour assessment (CT or MRI Scans)	X						X c			X		X c	6.9.1
Tumour marker	X						X c			X		X c	6.9.2
PK f		X	X	X	X	X	X	X g	X g	X	X		6.5
Anti-MEDI-573 Antibodies		X					X				X	X	6.5.3
Blood Biomarker Analysis		X	X	X	X	X	X	X	X	X	X		6.7

Date

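### In Cohorts 1 and 2 the Cycle 2 Day 1 window allows a fourth infusion on Day 21, inside the DLT window, and its early limit (Day 20) contradicts the 6-day minimum interval

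*Protocol*

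**What the plan says.** Four parts of the protocol bear on when the fourth weekly infusion may be given in Cohorts 1 and 2.

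- **Dosing days.** Section 3.1 puts the weekly infusions on Days 1, 8 and 15 of a 21-day cycle. Table 5 gives the Cycle 1 visits no allowance, and Section 5.1.8 rules out delay or modification in Cycle 1. The third dose is therefore on Day 15.
- **Visit allowance.** Table 5 gives Day 1 of Cycle 2 and beyond an allowance of ±2 days. Table 9, for Cohort 3, gives the same visit +2 only.
- **Minimum interval.** From Cycle 2 on, Section 5.1.8 says the "dosing interval should be 6 days or longer in Cohorts 1 and 2, and 20 days or longer in Cohort 3".
- **DLT window.** Under Section 5.1.4, DLT "will be assessed from Cycle 1, Day 1 through Cycle 1, Day 21". Section 5.1.7 gives the dose escalation committee the same Days 1 to 21. For evaluability, Section 5.1.6 asks for three doses in Cohorts 1 and 2 and 21 days of follow-up counted from the first dose.

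Escalation follows the 3+3 rule in Section 5.1.3. One DLT among three subjects adds three more. "If only one DLT is observed in the complete cohort of 6 evaluable subjects", escalation may go ahead. Two or more among up to six make the dose not tolerated.

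**The concern.** The Cycle 2 Day 1 window in Table 5 opens before the DLT window has closed, and part of it is ruled out by the protocol's own minimum interval.

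**Day 21.** A subject dosed on this day has had four infusions within the period that is meant to judge three. Table 5 schedules no Cycle 1 visit after Day 15, so Cycle 2 Day 1 is the next planned safety check. Held on Day 21, it re-doses the subject before the assessment period has ended. If that infusion causes an acute Grade 3 or higher reaction, the event is in the window by date and in Cycle 2 by dose. Sections 5.1.4 and 5.1.6 count partly by cycle label and partly by days from the first dose, and they do not say which governs. Section 5.1.6 makes a subject unevaluable for a delayed dose but is silent on an early one.

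**Day 20.** A site that schedules from Table 5 alone could dose on this day and break the interval in Section 5.1.8.

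In a 3+3 design single events decide, so whether one event counts can change whether a cohort is expanded or a dose declared not tolerated.

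**Working it through.** **1. Calendar for Cohorts 1 and 2.** With a 21-day cycle, Cycle 2 Day 1 is nominally Day 1 + 21 = Day 22, which is 22 − 15 = 7 days after the third dose. Each day allowed by Table 5 (22 ± 2) was checked against the 6-day minimum and the DLT window (Day 21 or earlier):

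| Offset | Study day | Days since Day 15 dose | Meets 6-day minimum | Inside DLT window |
|---|---|---|---|---|
| −2 | 20 | 5 | no | yes |
| −1 | 21 | 6 | yes | yes |
| 0 | 22 | 7 | yes | no |
| +1 | 23 | 8 | yes | no |
| +2 | 24 | 9 | yes | no |

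Two of the five permitted days are faulty: Day 20 breaks Section 5.1.8, and Day 21 satisfies both rules but overlaps the window. Because Day 15 cannot move, the −2 limit can never be used at this visit without a breach.

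**2. Cohort 3 for comparison.** The previous dose is on Day 1, so the 20-day minimum alone would also admit Day 21 (21 − 1 = 20). The +2-only allowance in Table 9 restricts dosing to Days 22 to 24, so there is no overlap.

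**3. Effect on escalation (illustration).** The protocol gives no figure for this, so two inputs are assumed: a true Cycle 1 DLT probability p of 10 to 30%, and a probability q of 1 to 2% that a Day 21 infusion produces an acute event counted as a DLT.

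Under the 3+3 rule, P(escalate) = (1 − p)³ + 3p(1 − p)²(1 − p)³ = (1 − p)³ + 3p(1 − p)⁵.

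A subject dosed on Day 21 has p′ = 1 − (1 − p)(1 − q). If every subject is dosed that day, p′ replaces p throughout. If only one of the first three is, P(escalate) = (1 − p)²(1 − p′) + [p′(1 − p)² + 2p(1 − p)(1 − p′)](1 − p)³.

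Example with p = 0.20: 0.8³ + 3 × 0.2 × 0.8⁵ = 0.512 + 0.1966 = 0.709. With q = 0.01, p′ = 1 − 0.8 × 0.99 = 0.208, which gives 0.691 if all subjects are affected.

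| p | No Day 21 dosing | One subject, q = 1% | One subject, q = 2% | All subjects, q = 1% | All subjects, q = 2% |
|---|---|---|---|---|---|
| 0.10 | 0.906 | 0.903 | 0.900 | 0.891 | 0.875 |
| 0.20 | 0.709 | 0.705 | 0.701 | 0.691 | 0.674 |
| 0.30 | 0.494 | 0.491 | 0.488 | 0.480 | 0.466 |

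Computed before rounding, the loss is 0.3 to 0.8 percentage points with one subject affected and 1.4 to 3.5 points with all.

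**4. Later weekly doses.** With offsets a and b from −2 to +2 on two consecutive doses, the interval is 7 + b − a days. It is below 6 when a − b ≥ 2, which holds for 3 + 2 + 1 = 6 of the 25 pairs. This has no bearing on escalation, but it shows the same mismatch between Table 5 and Section 5.1.8.

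**The case against.** Five points can be made against this.

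- **The DLT text names Cycle 1.** An event after the infusion labelled Cycle 2 Day 1 would then naturally be a Cycle 2 event. This is a fair reading, but Section 5.1.6 also counts 21 days from the first dose, so Day 21 can carry both labels. The ambiguity is narrow and real.
- **Starting Cycle 2 on Day 21 shortens Cycle 1, and Section 5.1.8 forbids modifying Cycle 1.** That is arguable, but the ban does not clearly override an allowance that Table 5 prints for the Cycle 2 visit.
- **A visit window and a dosing minimum are two constraints, and a site must obey both.** This answers Day 20 for a site that reads both places. It leaves Day 21 open, and at Cycle 2 Day 1 the −2 limit remains unusable. Reading the interval rule as covering only doses within a later cycle does not help either: the 20-day rule for Cohort 3 can only be a gap between cycles, and without the rule Day 20 would join the overlap.
- **Serious acute events are acted on whatever their label.** This stands. Anaphylaxis stops dosing and entry pending committee review (Section 5.4.2), Grade 3 or greater infusion reactions end treatment for the subject, and laboratory tests on a dosing day are taken before the infusion. Patient protection is therefore not the main issue.
- **The effect is small and conservative.** This stands too. Section 2.2.2 reports no DLT in 25 US subjects, 14 of them at the two weekly doses used here (4 at 5.0 mg/kg and 10 at 15 mg/kg).

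**Conclusion.** The concern holds for Cohorts 1 and 2 only. The schedule permits one day of overlap between Cycle 2 dosing and the DLT window (Day 21), and one further day (Day 20) on which Table 5 contradicts Section 5.1.8. This part rests on calendar arithmetic and needs no assumption.

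The consequence is limited to acute events on Day 21, arises only if a site uses the early day, and leans toward not escalating if such events are counted. The losses in escalation probability are illustrations that depend on the assumed p and q. The upper figure of 3.5 points requires every subject to be dosed a day early. No planned sample size or DLT threshold is affected.

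It should still be corrected, because the dosing window is wrong as written and tolerability is the primary objective.

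**What to change.** Make three changes:

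1. In Table 5, change the allowance for Cycle 2 Day 1 from ±2 to +2, as Table 9 has it for Cohort 3.
2. In Section 5.1.8, state that no Cycle 2 dose is given before Day 22.
3. Add a footnote to Table 5 that the later ±2 windows are subject to the 6-day minimum, counted from the previous actual dose.

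The first two changes close the overlap and remove Day 20. No rule for classifying a Day 21 event is then needed, because such a dose cannot occur under the protocol. The cost is one table cell, one sentence and one footnote. Sites lose one usable scheduling day at Cycle 2 Day 1: Days 22 to 24 instead of 21 to 24.
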